5.3.2.2 Sampling for ADA/Nab assessment

For ADA assessment, blood will be taken from a forearm vein into a K2EDTA anticoagulant blood-drawing tube at the time points listed in the [Flow Chart](#) under ADA/Nab. For Nab assessment, blood will be taken from a forearm vein into a serum blood-drawing tube at the

time points listed in the Flow Chart under ADA/Nab. Handling procedures can be found in the laboratory manual (see ISF).

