6.4 SUBJECT SETS ANALYSED

The following analysis sets will be defined for this trial:

Enrolled Set (ES)

This patient set includes all patients who signed informed consent. It will be used for analyses of patient disposition.

Safety Analysis Set (SAF):

This patient set includes all patients who received at least one dose of study drug in trial 1368-0067. This is the main analysis set for efficacy and safety. Patients will be analyzed according to the actual treatment received.

Safety Set ADA (SAF-ADA)

This patient set includes all patients who received at least one dose of study drug and had at least one evaluable ADA sample in trial 1368-0067. This is the main analysis set for ADA impact on efficacy and safety. Patients will be analyzed according to the actual treatment received.

The discussion of all exceptional cases and problems and the decisions on the allocation of patients to populations will be made at the RPM/DBLM at the latest.

Table 6.4: 1 Overview of use of patient analysis sets by class of endpoint and handling of estimand and missing data

Class of endpoint	
	ES SAF
Disposition	OR
Compliance and exposure	OR
iPD	OR
Demographic/baseline characteristics	OR
Concomitant medication	OR
Primary endpoint	OR
Secondary binary efficacy endpoints	OC-NRI: for binary efficacy endpoints
Secondary continuous efficacy endpoints	OC for continuous efficacy endpoints.
Further efficacy endpoints	OC for continuous efficacy endpoints. OC-NRI: for binary efficacy endpoints
Plasma concentration & ADA	OR
Efficacy endpoints by ADA impact	OC for continuous efficacy endpoints OC-NRI for binary efficacy endpoints
AE	OR
Lab data, vital signs	OC-IR

For explanation of the different approaches with regard to missing data see [Section 6.6](#).

[figure not shown]
OC = observed cases excluding values after any use of rescue medication.

OC-IR = observed cases including also values after any use of rescue medication.

OC-NRI = values after any use of rescue medication will be censored and impute with non-responder..

OR = original results.

NRI = Non-Response Imputation, cf. [Section 6.6.2](#).

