7.9.2 Immunogenicity

Analysis of ADA and assessments of ADA impact on PK will be performed based on the complete administration data of spesolimab from both 1368-0052 and this trial data 1368-0067. Analysis of assessments of ADA impacts on safety and efficacy endpoints will be performed based on this 1368-0067 trial data only for the clinical trial report (CTR).

The ADA status and titre as well as frequency of patients with ADA to spesolimab will be presented by visit. Descriptive statistics of ADA titre (for ADA positive patients, when available) will be provided by visit. The number of subjects with ADA status positive/negative at any time will also be presented. ADA parameters (e.g. treatment-induced ADA positive subjects, transient ADA response and persistent ADA response) will also be presented by visit and cumulatively for the overall study duration. Further exploratory assessments of the ADA data will be performed once data are available and these will be described, if done, in the CTR.

Further analyses based on ADA data will be performed for efficacy-based and safety-based analysis with the following ADA and neutralizing antibody (NAb) status and endpoints.

Patient is considered ADA positive (+) if he/she had at least 1 positive ADA sample in the trial. Otherwise, patient is considered ADA negative (-). Patient is considered NAb positive (+) if he/she had ADA positive and at least 1 NAb positive sample in the trial. Patient is considered NAb negative (-) if he/she had ADA positive but no NAb positive sample OR if he/she is considered ADA negative.

- efficacy-based subgroup analysis as described in [Section 6.4](#)
 - ADA positive and ADA negative subjects (at Week 12 or later time), or
 - Neutralising antibody (Nab) positive and NAb negative subjects (at Week 12 or later time)
- Safety-based subgroup analysis (using e.g. hypersensitivity safety events)
 - ADA positive and ADA negative subjects (at any time), or
 - NAb positive and NAb negative subjects (at any time), or before ADA development (including subjects with events either before their first ADA positive sample or without ADA positive sample throughout) and after ADA development (including subjects with events from the time point of their first ADA positive sample onwards). This approach takes into account the time when ADA actually developed and when the safety event occurred in relationship to ADA.

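### The two-level NAb split in SAP 7.9.2 cannot separate neutralisation from the presence of ADA, and it counts a missing NAb result as negative

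*SAP*

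**What the plan says.** SAP 7.9.2 (Immunogenicity) sets antibody status per patient. A patient with at least one positive ADA sample in the trial is ADA-positive. For everyone else, "Otherwise, patient is considered ADA negative". On neutralising antibodies it says "Patient is considered NAb positive (+) if he/she had ADA positive and at least 1 NAb positive sample in the trial", and then "Patient is considered NAb negative (-) if he/she had ADA positive but no NAb positive sample OR if he/she is considered ADA negative".

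Two efficacy splits are listed, joined by *or*: "ADA positive and ADA negative subjects (at Week 12 or later time), or" followed by "Neutralising antibody (Nab) positive and NAb negative subjects (at Week 12 or later time"). The safety splits have the same form, and a before/after-ADA-development comparison is added. No split of ADA-positive patients by NAb status is listed, and there is no category for a missing NAb result.

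The analysis set for ADA impact, SAF-ADA in SAP 6.4, requires that a patient was dosed and "had at least one evaluable ADA sample in trial 1368-0067". It does not require an evaluable NAb sample. Protocol 5.3.2.2 collects ADA in a K2EDTA tube, and for NAb it states: "For Nab assessment, blood will be taken from a forearm vein into a serum blood-drawing tube". ADA and NAb share one row in each Flow Chart, so they are drawn at the same time points.

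The frequency output named in SAP 7.9.2 is for ADA: "The ADA status and titre as well as frequency of patients with ADA to spesolimab will be presented by visit". No NAb frequency table is named.

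**The concern.** The NAb-negative level holds up to three different kinds of patient: those without ADA, those with ADA who were tested and found non-neutralising, and those with ADA but no NAb result. The last group falls in because having no positive NAb sample is also true of a patient with no NAb sample at all.

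The NAb-positive level holds only ADA-positive patients. Comparing the two levels therefore largely repeats the ADA-positive versus ADA-negative comparison under another name. The group needed to judge neutralisation, ADA-positive and NAb-negative, is never shown alone.

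A lower response or more hypersensitivity among NAb-positive patients could then be read as an effect of neutralisation when it reflects only the presence of ADA, or whatever goes with ADA. In a trial without hypothesis tests, readers depend on the group labels.

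**Working it through.** The documents state no ADA rate, NAb rate, missing rate or ADA effect, so there is no planned figure to reproduce. The check uses mixture arithmetic on assumed values.

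**Inputs**
- From the documents: about 45 patients (Protocol synopsis) and the definitions in SAP 7.9.2.
- Assumed: share ADA-positive p = 0.20 to 0.50; share of those NAb-positive q = 0.30 to 0.70; share of truly NAb-positive patients without a NAb result m = 0 or 0.20; ADA effect on response d = 0, -10 or -20 points; neutralisation effect 0.

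**Step 1: composition of the NAb-negative group.** The share of that group that is ADA-negative is

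s = (1 - p) / (1 - p·q·(1 - m)).

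**Step 2: expected difference.** Let r be response without ADA. NAb-positive patients respond at r + d. The NAb-negative group responds at r + d·(1 - s). The difference is d·s, although neutralisation does nothing.

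| p | q | m | s | d = -20 points | d = -10 points | d = 0 |
|---|---|---|---|---|---|---|
| 0.20 | 0.70 | 0 | 0.80/0.86 = 0.930 | -18.6 | -9.3 | 0 |
| 0.35 | 0.50 | 0 | 0.65/0.825 = 0.788 | -15.8 | -7.9 | 0 |
| 0.35 | 0.50 | 0.20 | 0.65/0.86 = 0.756 | -15.1 | -7.6 | 0 |
| 0.50 | 0.30 | 0 | 0.50/0.85 = 0.588 | -11.8 | -5.9 | 0 |
| 0.50 | 0.30 | 0.20 | 0.50/0.88 = 0.568 | -11.4 | -5.7 | 0 |

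The first and last rows are the extremes of the assumed range. ADA-negative patients make up 57% to 93% of the NAb-negative group.

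**Step 3: an example in patients (assumed).** Take 45 patients, 18 of them ADA-positive and 9 of those NAb-positive. Response is 60% without ADA and 40% with ADA, whatever the NAb status. The NAb-negative group responds at (27 × 0.60 + 9 × 0.40)/36 = 19.8/36 = 55%, against 40% in the NAb-positive group. The table shows a 15-point gap; within ADA-positive patients the gap is 40% - 40% = 0.

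**Step 4: missing NAb results.** The apparent NAb-positive share among ADA-positive patients is q·(1 - m). With m = 0 it is correct. With q = 0.50 and m = 0.20 it is 40% instead of 50%; at p = 0.35 that is 14.0% instead of 17.5% of all patients. Counting ADA-negative patients as NAb-negative does not change the NAb-positive count.

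Missing results also dilute a real effect, but only slightly. With a 20-point neutralisation effect, no effect of ADA itself and m = 0.20, the two-level table shows 20 × [1 - p·q·m/(1 - p·q·(1 - m))]. That is 20 × (1 - 0.012/0.952) = 19.7 points at p = 0.20, q = 0.30, and 20 × (1 - 0.07/0.72) = 18.1 points at p = 0.50, q = 0.70.

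**Step 5: after regrouping.** Comparing NAb status within ADA-positive patients gives (r + d) - (r + d) = 0 in every scenario above. The NAb frequency among ADA-positive patients with a result equals q, if results are missing at random.

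**Step 6: cell size.** The NAb-positive group would hold 45·p·q·(1 - m) patients, from 45 × 0.20 × 0.30 × 0.80 = 2.2 to 45 × 0.50 × 0.70 = 15.8.

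**The case against.** **The missing cell can be recovered.** If the ADA and NAb tables are both produced for the same patients and visit, the ADA-positive/NAb-negative cell follows by subtraction. In the example, 7.2/18 less 3.6/9 leaves 3.6/9 = 40%, and the null contrast is visible. This stands for counts and means. It fails for medians and quartiles, which SAP 7 lists among its standard summaries. It also depends on both tables being produced, which the *or* between the splits does not guarantee, and patients without a NAb result would remain in the derived cell.

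**The SAP does not claim to isolate neutralisation.** True: it speaks of ADA impact, and NAb-positive patients against all others is a legitimate descriptive contrast. But a table headed by NAb status invites the other reading, and nothing in the plan warns against it.

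**Missing NAb status at patient level is speculative.** Largely true. ADA and NAb are drawn together at several visits, and one positive sample is enough. A truly NAb-positive patient is misclassified only if every sample that would have been positive lacks a result. The separate tube and the SAF-ADA definition show that this can happen, not that it will happen often.

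**The artefact needs an ADA-outcome link.** True, and the documents do not show one. They do leave room for it. One positive sample at any time makes a patient ADA-positive, so longer follow-up gives more chances, while Protocol 3.3.4.1 stops certain non-responders at Week 24. SAP 5 uses a different efficacy baseline by parent-trial arm, and prior-spesolimab patients have had longer exposure.

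**Little depends on it.** True: the analysis is descriptive, without confirmatory testing, in about 45 patients, and the primary endpoint is TEAEs. The cells after regrouping will be small.

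**Conclusion.** The concern holds in a conditional form. The NAb comparison as defined cannot separate neutralisation from the presence of ADA, and any missing NAb result is scored as negative. With neutralisation inert, the expected NAb difference is 57% to 93% of whatever ADA difference exists: 11 to 19 points for an assumed 20-point ADA effect and 6 to 9 for 10 points. All rates are assumptions, because the documents give none.

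A reader might infer two stronger things that the documents do not support:
- **That the table will show a NAb effect even when neutralisation has none.** This happens only if ADA status is itself related to outcome; otherwise the expected difference is 0.
- **That NAb frequency is understated.** This needs missing NAb results. The documents give no missing rate, sample NAb alongside ADA, and name no NAb frequency table.

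This is a cheap improvement to a descriptive analysis. It does not affect the primary safety conclusion.

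**What to change.** In SAP 7.9.2:
- Present efficacy and safety in these groups: ADA-negative; ADA-positive/NAb-negative, requiring at least one evaluable NAb result and none positive; and ADA-positive/NAb-positive.
- Show ADA-positive patients without an evaluable NAb result as *NAb not evaluable*, and leave them out of the NAb contrast.
- Make the NAb comparison within ADA-positive patients.
- If a NAb frequency is reported, use ADA-positive patients with an evaluable NAb result as the denominator.

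No new data are needed. The cost is SAP wording and one or two extra columns. The two-level split can still be obtained by adding columns together. The downside is small cells, so the within-ADA-positive contrast will be imprecise and should be shown with counts.

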4.2.1.1 Systemic hypersensitivity including infusion reaction and anaphylactic reaction

In case of systemic hypersensitivity including infusion reaction and anaphylactic reaction emerging during or after infusion / injection(s) of trial medication, the investigator should consider in accordance with severity of the reaction and local SoC to:

- Immediately interrupt the infusion (if i.v.) or stop further injections (if s.c.).
- Treat with systemic anti-histamines, i.v. steroids, and in case of a severe allergic reaction (e.g., anaphylactic reaction) epinephrine.
- In case of s.c. administration give epinephrine in case of signs of hypersensitivity and add further treatments, e.g. oxygen, i.v. fluids, antihistamines and systemic corticosteroids as needed.

Also draw a plasma sample for IgE and ADA as detailed in the Lab Manual in the ISF (Central laboratory). Consider also the evaluation of histamine, serum tryptase, and complement components.

In case of infusion reaction, based on patient's clinical course and medical judgment, the infusion may be re-initiated in case of mild or moderate infusion reactions (according to Rheumatology Common Toxicity Criteria (RCTC) grading) at lower speed with gradual increase to complete the infusion as detailed in the Instructions for Pharmacist in the ISF. In any case, the total duration of infusion should not exceed 180 minutes (3 hours). If the infusion exceeds 180 minutes, it should be stopped and the infusion should be skipped. Patient should be called for the next scheduled visit as planned.

In case of systemic hypersensitivity, based on patient's clinical course and medical judgment, the injection(s) may be continued in case of mild or moderate systemic hypersensitivity

(according to RCTC grading) to complete the injections as detailed in the Instructions for Use of Spesolimab Pre-filled Syringes in the ISF.

In case of anaphylactic reaction based on the criteria discussed in the statement paper from Sampson HA ([Appendix 10.1 \[R11-4890\]](#)) suspected to be caused by the trial medication, the investigator should discontinue treatment permanently with spesolimab.

When a non-acute hypersensitivity reaction related to immune complexes (i.e., serum sickness) is suspected, please draw a sample for the laboratory assessment for circulating immune complexes.

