6.6 HANDLING OF MISSING DATA AND OUTLIERS

Section 7.3 of the CTP describes the handling of missing data.

The original results (OR) approach implies the presentation of data exactly as observed (not using time windows and not setting values to missing).

OR analysis will be performed on parameters and endpoints that are either not affected by patients' rescue therapy use (e.g., plasma concentration level of spesolimab, rescue therapy itself), or, it is not meaningful to apply any imputation rule for the replacement of missing values.

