7.8.1 Adverse Events

AEs will be coded with the most recent version of MedDRA.

For AEs in current trial, we will summarize AEs start in 1368-0052 and still ongoing in current trial 1368-0067 plus new AEs start in current trial.

The analyses of AEs will be descriptive in nature. All analyses of AEs will be based on the number of patients with AEs and not on the number of AEs. System organ classes (SOC, if applicable) will be sorted according to the standard sort order specified by the EMA, preferred terms (PT, if applicable) will be sorted by total frequency (within SOC).

For details on summarization of AE data, please refer to "Handling and summarization of adverse event data for clinical trial reports and integrated summaries" ([15](#)) and "Handling of missing and incomplete AE dates" ([10](#)).

The analysis of AEs will be based on the concept of TEAEs. This means that all AEs will be assigned to the screening period, on-treatment period (i.e. treatment phase plus REP) or off-treatment period (i.e. follow up) as defined in [Section 6.1](#). Since only the start date of an AE is collected (without start time), any AE occurrence on the same day as the first spesolimab administration will be assigned to the on-treatment phase.

Exposure-adjusted adverse event incidence rates for TEAE will be calculated using the following approach:

- 1) The exposure adjusted incidence rate (per 100 subject years) of a selected TEAE is defined as the number of subjects experiencing the adverse event per treatment group during time at risk divided by the total time of subjects at risk to contribute the event to the analysis multiplied by 100 (per 100 subject years), where:

Time at risk [subject years] = (date of onset of AE – first treatment start date in current study +1) / 365.25

- 2) If, for a subject, the selected TEAE didn't occur, then the time at risk will be censored at min (date of death, last contact date per EoS page, cut-off date for the interim analysis, or the end of on-treatment period). For each selected TEAE, the exposure adjusted incidence rate will be calculated as:

Incidence rate [1/100 Subject years (pt-yrs)] = 100 * number of subjects with TEAE / Total TEAE-specific time at risk [subject years].

An overall summary of AEs will be presented. This overall summary will include summary statistics for the class of other significant AEs (sponsor definition based on ICH E3) and for the class of AESIs.

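### Event-triggered ADA samples count towards ADA status and onset in SAP 7.9.2, which can inflate the apparent ADA-hypersensitivity association when rates are compared

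*SAP*

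**What the plan says.** **Protocol 4.2.1.1.** The trigger is stated as "In case of systemic hypersensitivity including infusion reaction and anaphylactic reaction emerging during or after infusion / injection(s) of trial medication". For these cases the section continues: "Also draw a plasma sample for IgE and ADA as detailed in the Lab Manual in the ISF (Central laboratory". Routine ADA samples follow the Flow Charts: Visits 1, 2, 3, 5 and 7 up to Week 12, then listed weeks (redacted), EoT and EoS.

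**SAP 7.9.2.** On patient status: "Patient is considered ADA positive (+) if he/she had at least 1 positive ADA sample in the trial". One of the planned analyses is a "Safety-based subgroup analysis (using e.g. hypersensitivity safety events". It may be split by ADA or NAb status at any time, or by period. The first period is "before ADA development (including subjects with events either before their first ADA positive sample or without ADA positive sample throughout". The second is "after ADA development (including subjects with events from the time point of their first ADA positive sample onwards".

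**SAP 6.4 and 6.6.** Table 6.4: 1 puts ADA under the original-results approach, described as "presentation of data exactly as observed (not using time windows and not setting values to missing".

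**SAP 7.8.1.** "Since only the start date of an AE is collected (without start time", so an event and a sample on the same day cannot be put in order.

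Neither document excludes or flags event-triggered ADA samples. Neither says outright that they enter the ADA analysis dataset. SAP 7.9.2 gives no denominator for the before/after split.

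**The concern.** The outcome prompts the test for the exposure. A patient with a systemic reaction is tested because of it. If that sample is the first positive one, the reaction falls in the after period by definition. A patient with the same undetected ADA and no reaction stays in the before period until the next scheduled sample. Events are then classed by current ADA status, while event-free time is classed by a delayed status. A comparison of rates mixes the two.

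The ever-positive split has a related weakness. If ADA comes and goes between scheduled samples, it is recorded only in patients who happened to react while it was present.

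Systemic hypersensitivity is an adverse event of special interest, long-term safety is the primary objective, and SAP section 3 foresees the data supporting submissions, Investigator's Brochure updates and publications. An association partly produced by the sampling rule could be read as a drug finding.

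**Working it through.** The plan has no figure to reproduce: it gives no ADA rate, reaction rate or sample size calculation. The check asks what the displays would show if ADA had no effect.

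**Assumptions (not in the documents unless stated)**
- Follow-up of 120 weeks: 104 for the two-year treatment plus the stated 16-week residual effect period.
- Scheduled samples at Weeks 0, 2, 4, 8 and 12 (the marked visits, if two weeks apart), then every 12, 24 or 36 weeks, plus Weeks 104 and 120.
- ADA incidence f of 30% or 50%; perfect assay.
- First reaction at 8 per 100 patient-years, independent of ADA; every reaction triggers a sample.

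**1. Before/after rate ratio, persistent ADA, onset uniform over Weeks 0-52**

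Mean true ADA time per developer is 120 − 26 = 94 weeks. Let L be the mean delay from onset to the next scheduled sample. An interval of w weeks contributes w²/2, and the first four intervals (2, 2, 4 and 4 weeks) contribute 20.
- 12-weekly: (20 + 3×72 + 4×10)/52 = 276/52 = 5.31 weeks
- 24-weekly: (20 + 288 + 16×16)/52 = 564/52 = 10.85 weeks
- 36-weekly: (20 + 648 + 4×34)/52 = 804/52 = 15.46 weeks

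Per patient, with scheduled samples only, time after is A = f(94 − L), time before is B = 120 − A, and undetected ADA time is U = fL. Triggered samples move the events that occur in U from before to after, but move almost no person-time. Hence

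ratio ≈ [(A + U)/A] ÷ [(B − U)/B].

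| Sampling | f | A | U | B | Ratio |
|---|---|---|---|---|---|
| 12-weekly | 0.3 | 26.61 | 1.59 | 93.39 | 1.08 |
| 12-weekly | 0.5 | 44.35 | 2.65 | 75.65 | 1.10 |
| 24-weekly | 0.3 | 24.95 | 3.25 | 95.05 | 1.17 |
| 24-weekly | 0.5 | 41.58 | 5.42 | 78.42 | 1.21 |
| 36-weekly | 0.3 | 23.56 | 4.64 | 96.44 | 1.26 |
| 36-weekly | 0.5 | 39.27 | 7.73 | 80.73 | 1.32 |

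The before group includes never-positive patients, as SAP 7.9.2 specifies. A simulation under the same assumptions gave 1.08-1.11, 1.18-1.22 and 1.27-1.34 with triggered samples, and 1.00 with scheduled samples only.

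**2. Ever-positive split**

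If ADA persists, a later scheduled sample finds it anyway, so the ratio stays at about 1.0.

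Now let ADA last 12 weeks, with onset uniform over Weeks 0-104. The fraction m of episodes lying wholly between scheduled samples is 0 at 12-weekly, 44/104 = 0.42 at 24-weekly and 56/104 = 0.54 at 36-weekly. Reaction risk is p = 1 − exp(−0.08 × 2.3) = 0.168; the chance of reacting during the episode is q = p × 12/120 = 0.0168.

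Ever-positive patients: N = f(1 − m) + fmq. Their events: E = f(1 − m)p + fmq. Ratio = (E/N) ÷ [(p − E)/(1 − N)].

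At 36-weekly with f = 0.5: N = 0.2308 + 0.0045 = 0.2353 and E = 0.0388 + 0.0045 = 0.0433, so the ratio is 0.184/0.163 = 1.13. With f = 0.3 it is 1.11. At 24-weekly it is 1.07-1.09, and at 12-weekly 1.00.

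**3. Plain counts, persistent ADA**

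The true share of developers' reactions that fall after onset is about 94/120 = 78%, and the triggered sample recovers it. Scheduled samples alone give (94 − L)/120 = 74%, 69% and 65%.

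**4. Scale in this trial**

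With about 45 patients, 45 × 0.168 ≈ 7.6 would react. The share of events reclassified is U/120, from 1.3% to 6.4%, or about 0.1 to 0.5 of one event.

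**The case against.** The strongest reply is that the triggered sample is right. A true positive on the day of a reaction is real ADA, and SAP 7.9.2 says the before/after split is meant to reflect when ADA actually developed. Calling such a reaction before ADA would be less accurate. For counts this stands, as step 3 shows, and it is why scheduled-only sampling should not simply replace the current rule.

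A second reply is that no rate is planned for this split. SAP 7.8.1 bases adverse event analyses on numbers of patients, and its exposure-adjusted rates are defined by treatment group. That is fair, but SAP 7.9.2 leaves the denominator open, and counts before and after ADA invite a comparison of rates.

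Third, the effect is small, the analysis is descriptive, and some patients cannot be affected. Those already positive at their first sample here are in the after period from the start. At visits with a scheduled pre-dose ADA sample, the extra draw adds little. All of this stands.

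A reader might also infer more than the documents support:
- **That every hypersensitivity event triggers a sample.** The trigger is a systemic reaction, whereas SAP Table 7.8.1: 1 finds hypersensitivity through separate narrow SMQ searches.
- **That the rule creates a false link in every split.** The ever-positive split is essentially unaffected if ADA persists.
- **That the bias is nearer 1.3, 1.6 and 1.9.** Setting f = 1 in step 1 gives those values, but that restricts the comparison to patients who develop ADA, and SAP 7.9.2 does not.

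**Conclusion.** The concern holds in a limited form. Patients with a systemic reaction get an ADA test that others do not, and no rule in the SAP flags or removes it. This can inflate a before/after comparison of rates per person-time and, if ADA is transient, the ever-positive comparison. Under no true effect the first ratio is about 1.1 to 1.3 across 12- to 36-weekly sampling. The second is about 1.0 with persistent ADA and up to about 1.13 with a 12-week duration. Counts of events after ADA are not inflated.

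The size rests on assumed ADA incidence, onset and duration, an assumed reaction rate, a perfect assay, and sampling weeks that are redacted. It also assumes that triggered results reach the ADA dataset, which the documents neither state nor rule out. The expected shift is under one event, but with so few reactions one reclassified event can change the displayed pattern, and no hypothesis test is planned. The change is worth making because it is cheap and makes outcome-driven detection visible.

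**What to change.** In SAP 7.9.2:

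1. Flag each ADA/NAb sample as scheduled or event-triggered.
2. Show the ADA and NAb safety splits and the before/after split twice: with all samples, and with scheduled samples only.
3. Base any rate or ever-positive comparison on scheduled samples.
4. List the triggered ADA/NAb result beside each reaction.
5. State the denominator of each display: patients or person-time.

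The cost is a few sentences, one flag on the ADA record, one extra display and a listing. No data are lost. The drawback is that, in the scheduled-only version, a reaction with a positive sample on the same day may appear as before ADA development; the all-samples version and the listing make that visible.

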Tabulations of frequencies for categorical data will include all possible categories and will display the number of observations in a category as well as the percentage (%) relative to the respective treated patient set. Percentages will be rounded to one decimal place. The category missing will be displayed if and only if there are actual missing values. Percentages will be based on all patients in the respective patient set whether they have non-missing values or not unless there is another particular specification.

Disposition of the patient population participating in the trial will be summarised by presentation of the frequency of patients enrolled, treated, enrolled but not treated, who completed all doses of trial medication as planned, who completed the trial (EOS), who prematurely discontinued study treatment, by reason and who withdrew from the trial, by reason. Summary statistics of patients who did the dose modification at Week 12 and patients who discontinued due to no change observed at Week 24 after dose modification (according to Table 3.1: 1 in CTP) will be also displayed. The frequency of patients with iPDs will be presented; iPDs will be listed per patient.

To better illustrate the long-term disposition of entire maintenance treatment (cf. [Section 6.1](#)), a summary table regarding patient status over time will be added. The cumulative frequency of patients for the following categories will be displayed based on ■-week intervals:

- Ongoing on study medication, i.e., without early treatment discontinuation by the time point
 - Intake of rescue medication
 - Up-titrate the dose to ■
 - Any of the above
- Pre-maturely stopped study medication, i.e., discontinued study medication by the time point
 - Intake of rescue medication
 - Up-titrate the dose to ■
 - Any of the above
- Ongoing but not achieved the visit, if due to the cut-off of interim analysis
 - Intake of rescue medication
 - Up-titrate the dose to ■

- Any of the above

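### The before/after ADA split in SAP 7.9.2 has no time at risk for either state, so unequal time can hide or reverse an association between antibodies and safety events

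*SAP*

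**What the plan says.** SAP 7.9.2 lists three ways to look at ADA and safety: ADA status at any time, neutralising-antibody status at any time, or a split at ADA development. The split has two states:

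- Before: "before ADA development (including subjects with events either before their first ADA positive sample or without ADA positive sample throughout".
- After: "after ADA development (including subjects with events from the time point of their first ADA positive sample onwards".

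The SAP explains its purpose thus: "This approach takes into account the time when ADA actually developed and when the safety event occurred in relationship to ADA". It gives no denominator and no time at risk for either state.

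The surrounding rules do not supply them:

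- SAP 7.8.1 sets the counting unit: "All analyses of AEs will be based on the number of patients with AEs and not on the number of AEs".
- SAP 7 sets the default denominator, unless otherwise specified: "Percentages will be based on all patients in the respective patient set whether they have non-missing values or not".
- SAP 6.4 makes SAF-ADA the main set for ADA impact on safety and efficacy.
- SAP 7.8.1 does define an exposure-adjusted incidence rate, as the "number of subjects experiencing the adverse event per treatment group during time at risk divided by the total time of subjects at risk". Its clock runs from the "first treatment start date in current study +1) / 365.25". Protocol 7.2.5 is similar. Neither section applies the rate by ADA state.

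**The concern.** The split respects the order of ADA and event but not the time available for events. A never-positive subject puts the whole on-treatment period into the before state. A converter puts in only the stretch up to the first positive sample. A subject already positive at the Visit 1 pre-dose sample, which is possible for patients from the parent trial's active arm, puts in almost none. Time in the two states is therefore unequal by construction, and a count of subjects with events mixes risk with duration.

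Safety is the primary objective. Systemic hypersensitivity is an adverse event of special interest (Protocol 5.2.6.1.4, SAP 7.8.1) and is the example that 7.9.2 gives for these subgroup analyses. The split is the only one of the three listed that uses timing. A reader could take a reassuring table as evidence that antibodies do not raise the risk when the table could look that way under a real doubling.

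**Working it through.** The documents give no ADA incidence, hypersensitivity rate or sample-size calculation for this trial, so there is no plan figure to reproduce. The check asks what the planned display would show under known truths.

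**Inputs from the documents.** N = 45 (Protocol synopsis and 3.3, approximate). Treatment lasts up to 2 years (Protocol 1.4.1), taken as 104 weeks. The residual effect period adds 16 weeks (Protocol 1.2.3). So T = 120 weeks = 120/52.18 = 2.30 years.

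**Assumptions, not in the documents.** Constant hazard λ = 0.10 per year before ADA and RR·λ after. A share f converts at week s. All subjects start ADA-negative and complete follow-up.

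**Formulas** (times in years):

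- Before, share of all subjects = (1−f)(1−exp(−λT)) + f(1−exp(−λs))
- After, share of all subjects = f(1−exp(−RR·λ(T−s)))
- After, share of subjects ever in the state = the same without the leading f. Everyone is at some time in the before state, so its percentage does not change.

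**Base case, f = 30%, s = 12 weeks.**

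- Total state time: before 45 × (0.7×120 + 0.3×12)/52.18 = 75.6 subject-years; after 45 × 0.3×108/52.18 = 27.9. The ratio is 2.7.
- Before: 0.7×0.205 + 0.3×0.023 = 15.1%, or 6.8 subjects.
- After, RR = 1: 0.3×0.187 = 5.6%, or 2.5 subjects. Ratio 0.37; truth 1.
- After, RR = 2: 0.3×0.339 = 10.2%, or 4.6 subjects. Ratio 0.68; truth 2.
- After, RR = 3: 0.3×0.463 = 13.9%, or 6.2 subjects. Ratio 0.92; truth 3.

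A simulation of 20,000 trials of the RR = 2 case gave 6.8 and 4.6 subjects, as the formula does.

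**Other denominator: percentage of subjects ever in the state, RR = 1.**

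| f | s (weeks) | Before | After | Ratio |
|---|---|---|---|---|
| 30% | 4 | 14.6% | 19.9% | 1.36 |
| 30% | 12 | 15.1% | 18.7% | 1.24 |
| 30% | 24 | 15.7% | 16.8% | 1.07 |
| 50% | 4 | 10.7% | 19.9% | 1.87 |
| 50% | 80 | 17.4% | 7.4% | 0.42 |

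**Range.** With RR = 1, λ from 0.05 to 0.20, f from 20% to 50% and s from 4 to 80 weeks, the ratio ran from 0.07 to 0.94 on counts or whole-set percentages. On in-state percentages it ran from 0.37 to 1.87.

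**With person-time by state.** If time in a state of length t stops at the first event there, expected time per subject is (1−exp(−λt))/λ, so events divided by time returns the hazard. The result is 10.0 against 10.0 per 100 subject-years for RR = 1, and 10.0 against 20.0 for RR = 2, in every scenario. The stopping rule matters. If ADA-free time were not stopped at the event, the before rate would be 6.8/75.6 = 9.0 per 100 against a correct 10.0 after, a false ratio of about 1.11.

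**The case against.** The strongest reply has four parts.

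- The analysis is exploratory. No test or decision rule depends on it, the trial has about 45 patients, and the split is one of three alternatives joined by *or*. This stands. It limits the weight of the point but does not supply the missing denominator.
- The SAP claims only that the split respects the order of ADA and event. This also stands. The sentence is true as far as it goes, but a reader could take it to mean that time has been handled.
- The SAP does not forbid person-time, leaves room for further ADA exploration, and nowhere says to apply the 7.8.1 clock to ADA states. True. The point is silence, not a wrong formula. That clock could not be used unchanged, because it would credit pre-ADA time to the after state.
- Person-time is not a full cure. If reactions cluster at early doses, time since first dose still confounds the comparison, and conversion is dated only to the sampling interval. True, and the report should say so.

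A reader might also infer that the split manufactures a very large false ADA risk. Among converters alone, with no true effect, 2.3% have an event before Week 12 and 18.7% after, about 8-fold (about 4-fold for conversion at Week 24, 26-fold at Week 4). The SAP's display does not support that reading. Its before state includes never-positive subjects, which brings those three cases to 1.24, 1.07 and 1.36 with 30% converting. A several-fold false excess would need nearly all subjects to convert early.

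**Conclusion.** The gap is real. SAP 7.9.2 defines no time at risk by ADA state, and no other section of the SAP or protocol fills it. On counts or whole-set percentages the expected distortion is masking or reversal: a null effect reads as 0.37 and a true doubling as 0.68 in the base case. On in-state percentages it can go either way, and a false excess stays modest, at most 1.87 over the range examined.

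These sizes rest on an assumed constant hazard, conversion share and conversion week, and on complete follow-up. The direction on counts depends less on them: across the range examined, the null ratio was always below 1. The point is worth settling before the final database lock, but no confirmatory conclusion is at risk.

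**What to change.** Add to SAP 7.9.2, on SAF-ADA, that each state is reported with the number of subjects with a first event in that state, the subject-years, and the exposure-adjusted incidence rate with 95% CI.

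- ADA-free time: from first dose in this trial to the earliest of first event in that state, first ADA-positive sample, or the 7.8.1 censoring points (death, last contact, interim cut-off, end of the on-treatment period).
- ADA-positive time: from first ADA-positive sample to the earlier of first event in that state or the same censoring points.
- A converter may contribute a first event to each state.
- Raw counts or proportions are not shown alone.
- A note states that the rates are exploratory, that time since first dose may still confound them, and that conversion dates are known only to the sampling interval.

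The cost is SAP wording and one derived time variable. No new data are needed. The intervals will be wide with about 45 patients, which is a reason to show them.
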